9.4. Expected toxicities of radiotherapy

The following are expected toxicities of radiotherapy.

- Fatigue
- Skin changes
- Difficulty swallowing (for those who receive nodal radiotherapy)
- Pneumonitis
- Breast oedema
- Breast tenderness
- Breast shrinkage
- Breast hardening
- Breast lymphoedema
- Arm lymphoedema
- Rib fracture
- Lung fibrosis
- Ischaemia heart disease
- Telangiectasia

Clinical judgement should be exercised when considering the expectedness of events in relation to radiotherapy.

9.5. Review of Serious Adverse Events

The Chief Investigator (or designated representative) will assess all reported SAEs for causality and expectedness (NB. The Chief Investigator cannot down-grade the Principal Investigator's assessment of causality).

SAEs assessed as having a causal relationship to study treatment and as being unexpected will undergo expedited reporting to the relevant authorities and all other interested parties by ICR-CTSU (see 10.6).

Sites should respond as soon as possible to requests from the Chief Investigator or designated representative (via ICR-CTSU) for further information that may be required for final assessment of an SAE.

9.6. Expedited Reporting of Related Unexpected SAEs

If an SAE is identified as being related to radiotherapy and unexpected by the Chief Investigator it will be reported by ICR-CTSU to the main REC, the Sponsor, and all other interested parties within 15 days of being notified of the event.

The Principal Investigators at all actively recruiting sites will be informed of any related unexpected SAEs occurring within the trial at appropriate intervals.

[figure not shown]
9.7. Follow up of Serious Adverse Events

SAEs should be followed up until clinical recovery is complete or until event has stabilised. SAE outcomes should be reported to ICR-CTSU using the relevant section of the SAE form in the database as soon as the Principal Investigator or designee becomes aware of the outcome.

9.8. Reporting Pregnancies

If any trial participant becomes pregnant while receiving trial treatment or up to 30 days after receiving trial treatment, this should be reported to ICR-CTSU using the pregnancy reporting form. Participants who become pregnant should discuss with their clinical team immediately. Where a clinician agrees appropriate to continue radiotherapy, the patient can remain in the trial. Pregnancies should be followed up until conclusion and all follow-up information should be reported to ICR-CTSU. If the outcome of the pregnancy meets the definition of serious (i.e. congenital abnormality) this should be reported to ICR-CTSU following the serious adverse event reporting procedures described above.

Figure 1: Flow diagram for SAE reporting, and action following report

NB. All SAEs should continue to be followed up as specified above

10. STATISTICAL CONSIDERATIONS

10.1. Statistical Design and Sample Size Justification

This is a multicentre, phase III, randomised trial with the primary aim of demonstrating non-inferiority of the 1-week schedules (test groups 1 and 2) when compared with the standard 3-week schedule (control) in terms of ipsilateral breast tumour recurrence rates at 5 years. Except where indicated, pairwise comparisons will be made between the control group and each of the two test groups.

Sample size for analysis of the primary endpoint.

5-year ipsilateral breast tumour recurrence in the control group is anticipated to be 3%. This has been estimated using information from IMPORT HIGH(6) and the expectation that the FAST-Forward Boost population will likely be a slightly higher risk group with recruitment of more participants with node positive disease. 4830 participants (randomised 1:1:1) provides 90% power to rule out a 2% absolute non-inferiority margin (i.e. ensuring 1-week SIB ipsilateral breast tumour recurrence rate is $\leq 5\%$ at 5 years). 5-year estimates will be based on Kaplan-Meier estimation with the corresponding critical hazard ratio being 1.68. The calculation allows for 5% loss to follow-up and a 2.5% alpha (1-sided) is used given the two comparisons being made (test group 1 vs control; test group 2 vs control).

Sample size for Early Side-Effects Sub-Study.

An assessment of acute toxicity (clinician- and patient-reported skin, breast and oesophageal symptoms measured using CTCAE v5.0 and PRO-CTCAE v5.0) will be performed with the aim of identifying any early safety signal with either of the test schedules. The primary endpoint for this analysis, on which the sample size is based, is clinician-reported CTCAE v5.0 skin toxicity. Grade ≥ 3 acute skin reactions are expected to be low, about 3% in the control group. The aim of this analysis will be to rule out $\geq 10\%$ acute skin reactions CTCAE v5.0 grade ≥ 3 in either test group. Based on an A'Hern single-stage design with 90% power and 5% one-sided significance level, this would require 103 participants in each of the test groups. The same number of patients will be included from the control group to confirm the design assumptions, but this will be a non-comparative analysis. Allowing for approximately 10% of patients missing the relevant assessment data (or excluded from the per protocol population on which this analysis will be based), approximately 345 patients will be included in this sub-study. If 6/103 or more participants within either test group have CTCAE v5.0 skin reactions \geq grade 3 then it would not be possible to exclude a 10% rate.

Sample size for subgroup analysis of pneumonitis rates in IMC population.

Acute lung toxicity is a specific consideration relevant to patients receiving radiotherapy to the IMC (expected to be 10-15% of recruited patients). As such, a powered subgroup analysis to evaluate this is planned. Based on RTOG assessment, the rate of $\geq G3$ pneumonitis occurring up to 3 months post-treatment in patients requiring radiotherapy to the IMC is anticipated to be 2% in the control group and we want to rule out an increase of 3% (to 5%) or more in the test groups. The two test groups will be combined for this analysis since the mean dose to the lung for both schedules is almost identical. Using an A'Hern single stage design with 90% power and a 5% one-sided significance level, 311 participants receiving IMC radiotherapy in either of the experimental arms would allow a rate $> 5\%$ to be ruled out. Rates of pneumonitis in control arm patients requiring IMC radiotherapy will be considered for the purpose of confirming the design assumptions but this will be a non-comparative analysis. If more than 9/311 cases of $\geq G3$ pneumonitis were reported in those receiving 5Fr SIB, then it would not be possible to exclude a rate of 5% or more.

Sample size for late normal tissue effects analysis.

Late normal tissue effects, and particularly breast induration, are important secondary endpoints of the trial. An analysis of clinician-assessed breast induration at 3 years is planned with the aim of demonstrating that there is not an unacceptable increase in risk of these symptoms associated with either of the test schedules. Based on IMPORT HIGH(6), we expect 11% of patients to have moderate/mark clinician-assessed breast induration by 3 years in the control group. A sample size of 823 patients per arm will provide 90% power to rule out an increase of 5% (to 16%) or more in either of the test groups (2.5% alpha for each pairwise comparison). This analysis will be based on the per protocol population. Allowing for approximately 20% of patients missing the relevant assessment data (or excluded from the per protocol population), the anticipated timing of this analysis is when 3090 patients have reached 3 years follow-up after randomisation.

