1. INTRODUCTION

1.1. Background/rationale for the trial

Radiotherapy is an important component of breast cancer treatment for many people: Breast cancer is the commonest cancer in the UK and radiotherapy is integral to the curative pathway for 37,000 UK people/year(1). Improvements in treatment, including radiotherapy and systemic therapies, have lowered disease recurrence rates but it remains the case that radiotherapy reduces the risk of local recurrence by up to two-thirds translating into improved breast cancer survival for the majority. Younger patients, and those whose disease expresses more aggressive biology, such as triple negative breast cancer, may have the most to gain from radiotherapy(2, 3) and are the population considered in this trial.

Radiotherapy impacts on the lives of people with breast cancer during treatment and for many years after cancer is cured: Radiotherapy can lead to early and long-term side-effects in breast and adjacent organs with impact on quality of life and wellbeing(2, 4). Acute side-effects include skin changes and fatigue which affect nearly all patients, peaking in the 2-4 weeks after radiotherapy. These tend to be mild for most patients. Symptomatic lung inflammation (pneumonitis) is rare (peaking around 3 months after radiotherapy in up to 2% of patients needing radiotherapy to lymph nodes behind the breastbone) but causes cough, breathlessness and fatigue when it occurs(5). Late breast radiotherapy side-effects include changes in breast appearance, notably breast shrinkage, which increase in incidence over time affecting around 16% people by 5 years(6). Lymphoedema affects 1 in 10 patients but can be lifelong when it occurs(5, 7). Major radiotherapy side-effects, including heart disease and second cancer, are rare (for example the risk of second lung cancer in non-smokers treated with modern radiotherapy techniques including breath-hold is <1 in 1000 at 20-years post-radiotherapy)(8).

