Timing of assessments (assuming no treatment interruptions*):

	Control Group	Test Group
Week 1	At fraction 5	At fraction 5
Week 2	At fraction 10	7 days after final fraction
Week 3	At fraction 15	14 days after final fraction
Week 4	7 days after final fraction	21 days after final fraction
Week 5	14 days after final fraction	28 days after final fraction
Week 6	21 days after final fraction	35 days after final fraction
Week 7	28 days after final fraction	42 days after final fraction

*In the unlikely event of treatment interruptions, the timing of these weekly assessments should remain scheduled in accordance with the originally planned start and end dates.

Month 3

The following assessments should be conducted at 3 months after the start of radiotherapy for all participants:

- Lung toxicity assessment (RTOG) (*can be conducted by remote consultation*)
- Participants who have consented to complete PRO questionnaires will be sent/given a Follow-up (e)PRO booklet, including the following questionnaires (*for UK participants this will be coordinated by ICR-CTSU*):
 - EORTC QLQ-C30 and QLQ-BR23
 - Body Image Scale (BIS)
 - Fatigue (EORTC QLQ FA12)
 - EQ-5D-5L

- Radiotherapy symptoms (breast & arm/shoulder trial specific, used in previous trials).
- Patient reported health care resource use (UK only)

Additional assessments at month 3 for EARLY SIDE-EFFECTS SUB-STUDY ONLY

Patients will be sent the sub study specific “Follow Up Assessments – 3 months” (e)PRO booklet, containing the following additional questionnaires (*this will be coordinated by ICR-CTSU*):

- Patient assessed skin, breast, and oesophageal toxicity assessment (PRO-CTCAE V5.0 and trial specific questions as used in previous trials).

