**Follow-up times are measured from treatment start date.*

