10.5. Interim Analyses and Stopping Rules

An Independent Data Monitoring Committee (IDMC) will be formed and will confidentially review accumulating safety and efficacy data from the trial at regular intervals (at least annually). Given the non-inferiority hypothesis, and that primary endpoint events will accrue slowly relative to recruitment timescales, early stopping on the basis of efficacy is not expected to be relevant and so no formal interim analysis or

stopping rules are in place. However, at each review, the IDMC will consider the balance of risks and benefits in the accumulating data, as well as any emerging external evidence, in making recommendations to the TSC regarding continuation of the trial.

At the time of analysis for the Early Side-Effects Sub-Study, if 6 or more participants (out of 103) within either test group have skin reactions \geq grade 3 (on CTCAE v5.0) then it would not be possible to exclude a 10% rate and this will provide stopping guidelines on which the IDMC will base their recommendations. PRO-CTCAE v5.0 data will also be considered. Similarly, for the subgroup analysis of IMC patients, 9 or more cases of RTOG \geq grade 3 pneumonitis in the first 311 IMC patients receiving 5Fr SIB (either test group) would mean a 5% rate could not be excluded and provides stopping guidelines on which the IDMC will base their recommendations. In both cases, consideration will also be given to the observed control arm rates for these toxicities and whether these align with design assumptions. Unless the IDMC advise otherwise, recruitment will continue whilst these analyses are undertaken.

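### The 2% control rate for grade 3 or higher pneumonitis by 3 months equals the background's upper figure for all symptomatic pneumonitis, so the fixed 5% ceiling may allow more than the stated 3-point increase

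*Protocol*

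**What the plan says.** Protocol section 10.1 plans a powered subgroup analysis of RTOG grade 3 or higher pneumonitis in IMC patients, with the two test groups pooled. Grade 3 or higher "pneumonitis occurring up to 3 months post-treatment in patients requiring radiotherapy to the IMC is anticipated to be 2% in the control group". The stated aim is to exclude a test-group rate of 5%, which is 3 points above that figure. The size is set so: "Using an A'Hern single stage design with 90% power and a 5% one-sided significance level, 311 participants receiving IMC radiotherapy". Control IMC patients serve only to check the design assumptions, in a non-comparative analysis.

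The background in section 1.1 describes symptomatic lung inflammation as rare, "peaking around 3 months after radiotherapy in up to 2% of patients needing radiotherapy to lymph nodes behind the breastbone".

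On timing, section 8.6 introduces the month 3 visit, which includes the RTOG lung assessment, with "The following assessments should be conducted at 3 months after the start of radiotherapy for all participants". The footnote to section 10.3 adds: "Follow-up times are measured from treatment start date". Section 10.4 confirms that this analysis uses the 3-month RTOG data. A further RTOG lung assessment takes place at year 1 (sections 8.7 and 10.3), outside the powered analysis.

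Two cut-offs appear. Section 10.1 says 5% cannot be excluded "If more than 9/311 cases of" grade 3 or higher pneumonitis are reported. Section 10.5 sets the guideline for the data monitoring committee (IDMC) at 9 or more cases of "pneumonitis in the first 311 IMC patients receiving 5Fr SIB (either test group) would mean a 5% rate could not be excluded".

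**The concern.** The same 2% describes two different events. In section 1.1 it is an upper figure for all symptomatic pneumonitis with no time limit. In section 10.1 it is the expected rate of grade 3 or higher pneumonitis alone, counted to a visit at about the stated peak, and no source is given. Fewer events should be expected when only the severe cases are counted and the count closes near the peak.

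This matters because the test groups are judged against a fixed 5%, not against the randomised controls. The 5% is described as a 3-point increase over control, which is true only if control is 2%. If control is lower, a larger increase fits under the ceiling. Section 1.1 says it is necessary to show that 1-week IMC radiotherapy brings no increase in pneumonitis, in a period when more patients receive drugs that can themselves cause it. Section 10.4 plans to publish the result early as reassurance.

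**Working it through.** **Inputs.** From section 10.1: p1 = 2%, p0 = 5%, one-sided alpha 5%, power 90%, n = 311, pass with at most 9 events. From section 10.5: fail at 9 or more, so pass with at most 8. From section 10.2: 1:1:1 allocation, with nodal need including IMC as a stratification factor. The documents give neither a grade 3 or higher rate separate from the symptomatic rate nor a time course, so any control rate other than 2% is an assumption.

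**1. The plan's own figure.** An exact binomial search for the smallest n with P(X ≤ k | n, 5%) ≤ 0.05 and P(X ≤ k | n, 2%) ≥ 0.90 gives n = 311, k = 9:
- P(X ≤ 9 | 311, 5%) = 0.0497
- P(X ≤ 9 | 311, 2%) = 0.902

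Section 10.1 is therefore reproduced.

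**2. The two cut-offs.** Under section 10.5:
- P(X ≤ 8 | 311, 5%) = 0.0252
- P(X ≤ 8 | 311, 2%) = 0.826

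Only the section 10.1 rule gives the stated 90% power; the section 10.5 rule gives 83%.

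**3. Where the window closes.** Take 3 months as 13 weeks from the start of radiotherapy. The test groups finish in week 1, so the visit falls about 13 − 1 = 12 weeks after the last fraction. Control finishes in week 3, so it falls about 13 − 3 = 10 weeks after. Section 1.1 puts the peak around 3 months after radiotherapy, so the window closes at or slightly before it.

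**4. What the ceiling allows if control is below 2%.** The chance of passing is P(X ≤ k | 311, true test rate in the window):

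| Assumed control rate | True test rate | Pass, at most 9 | Pass, at most 8 |
|---|---|---|---|
| 1% | 2% (doubling) | 90.2% | 82.6% |
| 1% | 3% (tripling) | 54.3% | 41.0% |
| 1% | 4% (fourfold) | 20.1% | 12.3% |
| 0.5% | 1.5% (tripling) | 98.0% | 95.3% |
| 0.5% | 2% (fourfold) | 90.2% | 82.6% |

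In absolute terms, with control at 1% the distance to the ceiling is 5 − 1 = 4 points, and with control at 0.5% it is 4.5 points, against the stated 3.

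**5. Can the control arm check the 2%?** With 1:1:1 allocation, 311 pooled test patients imply about 311 / 2 ≈ 155 control IMC patients. Expected events are 155 × 0.02 = 3.1 at a true 2%, 1.6 at 1% and 0.8 at 0.5%. The chance of two or fewer control events is 40%, 80% and 96% respectively. A low control count is common even when 2% is right, so it cannot separate 2% from 1%.

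**6. Precision of a randomised difference.** If both rates are 2%, the half-width of a 95% normal-approximation interval is 1.96 × √[0.02 × 0.98 × (1/311 + 1/155)] = 2.7 points. This is wide, but it addresses whether there is an increase.

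**The case against.** The strongest reply is that nothing is miscalculated. The 2% and the 5% both refer to grade 3 or higher events within the 3-month window, and for that hypothesis the error rates are as stated. This stands.

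The window is also deliberate: section 1.1 asks about pneumonitis within the first 3 months from treatment, and the objective is acute lung toxicity. The timing gap in the judged groups is about a week against a peak given only as around 3 months. The section 10.3 footnote belongs to asterisked items in that section, so it is the month 3 visit in section 8.6 that ties the lung assessment to the start of treatment. All this stands, and it makes severity the firmer half of the point.

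A reader might go further and infer that a true overall rate of 5% would wrongly be excluded with high probability because many cases arise after the visit. If 25%, 33% or 50% of cases came later, the chance of at most 9 events would be 27%, 40% or 75%. The documents do not support calling these error rates. The protocol states no hypothesis about an overall rate, and those late shares are assumptions. Nor do the documents establish that the in-window rate is well below 2%. That section 10.1 took its figure from section 1.1 is an inference from the matching number, and the newer systemic drugs named in section 1.1 could push the rate upward.

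Safeguards exist. Lung toxicity at 12 months is a secondary endpoint, section 10.4 plans between-group comparisons of toxicity frequencies, and the IDMC will consider control rates. None of these enters the decision rule, and step 5 shows how weak the control check is.

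**Conclusion.** The point holds as a mismatch between the assumed rate and the protocol's own background, not as an error in the sample size. On section 1.1, 2% is an upper figure for all symptomatic pneumonitis, so the rate of its severe subset by 3 months from the start may be lower. If it is, the fixed 5% ceiling allows more than the 3-point increase it is said to exclude. How much more depends on an unstated control rate: at an assumed 1%, a doubling passes 90% of the time and a tripling 54% under the section 10.1 rule. The control arm, at about 155 patients, cannot settle the matter. The size is thus illustrative; the inconsistency between sections 1.1 and 10.1 is not. Separately, sections 10.1 and 10.5 contradict each other on a count of exactly 9.

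**What to change.** Keep the 3-month analysis and its place in IDMC review, with these changes:

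1. Reconcile the 2% with section 1.1: give a source for the grade 3 or higher rate, or restate that rate and the ceiling, or apply the 2%/5% design to symptomatic pneumonitis, the event the background figure describes. Restating changes the size: 1% against 4% needs 227 patients (pass with at most 4), and 1% against 2.5% needs 675 (at most 10). The latter exceeds the 322 to 483 test-group IMC patients expected from 4830 × 10–15% × 2/3.
2. Report the randomised test-minus-control difference with its confidence interval in the IMC stratum, in place of a purely non-comparative analysis.
3. Report the scheduled year-1 RTOG lung result in the same patients as a supplementary analysis, and describe the 3-month result as covering that window only. Replacing the primary window with one year is not proposed: no 12-month rate is given, and later systemic therapy or fibrosis could blur the picture.
4. Reconcile the cut-offs in sections 10.1 and 10.5, and state the power of the rule kept.

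The cost is mainly wording and analysis, since both lung visits are already scheduled; a restated rate could change the number of patients needed. The full pneumonitis statement would come up to 9 months after the 3-month one, and the interval for the difference will be wide.

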Risks and benefits of 1-week radiotherapy for people with breast cancer who require treatment to the internal mammary chain (IMC): Patients requiring radiotherapy to nodes behind the breastbone (IMC) were not included in the FAST-Forward Nodal Sub-Study since data demonstrating a survival gain of IMC radiotherapy were only published more recently and therefore SOC for this patient group will remain as 3-week radiotherapy even beyond the FAST-Forward Nodal Sub-Study primary analysis(28). The population of patients eligible for FAST-Forward Boost (generally younger women and those with higher grade cancer more likely to have lymph node involvement) will be enriched for patients requiring IMC radiotherapy. This group is currently anticipated to make up 10-15% of the eligible population, with this proportion anticipated to increase following Lancet publication of a meta-analysis supporting the use of IMC radiotherapy in several patient subgroups with lymph node involvement(8). Whilst relative effects on local recurrence would be expected to be comparable to those seen in FAST-Forward and FAST-Forward Nodal Sub-Study, it remains necessary to demonstrate that 1-week IMC radiotherapy is not associated with any increase in lung toxicity (pneumonitis) within the first 3 months from treatment. This is especially pertinent in the modern era of breast cancer management where many patients are receiving increasing adjuvant systemic treatment (e.g. TDM-1, immunotherapy) of which pneumonitis is a recognised side effect. These treatments were not routinely given in the FAST- Forward/IMPORT HIGH recruitment period. FAST-Forward Boost will provide these data and can be extrapolated to those without boost since associated lung doses would be no higher.

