2. TRIAL OBJECTIVES

2.1. Trial Aim and Hypothesis

FAST-Forward Boost aims to establish a 1-week schedule of SIB radiotherapy as standard of care in patients undergoing radiotherapy for breast cancer +/- lymph nodes with a tumour bed boost. It hypothesises that local recurrence rates at 5-years will be no higher with appropriately dosed 1-week SIB radiotherapy than with 3-week SIB radiotherapy and that this can be achieved without an increase in normal tissue side-effects. A secondary aim is to characterise the pneumonitis rates in the subpopulation of patients who require internal mammary chain (IMC) radiotherapy, hypothesising that these are no higher for IMC radiotherapy delivered in 1-week as in 3-weeks.

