2.2. Trial Objectives

Specific objectives are:

1. To establish non-inferiority of 1-week SIB radiotherapy when compared with standard 3-week SIB radiotherapy in terms of local recurrence rates for the treatment of breast cancer requiring radiotherapy with a tumour bed boost.
2. To describe (long-term) clinical outcomes with 1-week SIB radiotherapy compared with 3-week SIB radiotherapy in this patient group
3. To evaluate acute toxicity with 1-week SIB radiotherapy compared with standard 3-week SIB radiotherapy specifically in relation to skin changes and tiredness.
4. To evaluate late effects of 1-week SIB radiotherapy compared with standard 3-week SIB radiotherapy, specifically chronic breast shrinkage, hardness, tenderness and cosmesis.
5. To establish rates of acute lung toxicity (pneumonitis) with 1-week SIB radiotherapy compared with standard 3-week SIB radiotherapy in patients receiving IMC radiotherapy.
6. To establish how early and late side-effects of 1-week versus 3-week SIB radiotherapy impact on patient-reported quality of life and on economic aspects.

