10.2. Treatment Allocation

All trial participants will receive radiotherapy.

Participants will be allocated between the three groups – control, test group 1 and test group 2 - on a 1:1:1 basis (open-label). Allocation will be by computer generated random permuted blocks. Randomisation will be stratified by:

- breast surgery type (breast conservation surgery (including mammoplasty) or breast conservation surgery with perforator flap reconstruction)
- need for nodal radiotherapy (none, nodes not including IMC or nodes including IMC)
- treating centre.

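### The IMC pneumonitis aim compares 1-week with 3-week radiotherapy, but its powered analysis is a single-arm test against a fixed 5% that matches the intended 3-point increase only if the control rate is 2%

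*Protocol*

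**What the plan says.** The question is put comparatively in three places in the protocol:

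- Section 1.1: "it remains necessary to demonstrate that 1-week IMC radiotherapy is not associated with any increase in lung toxicity (pneumonitis".
- Section 2.1, secondary aim: "hypothesising that these are no higher for IMC radiotherapy delivered in 1-week as in 3-weeks".
- Section 2.2, objective 5: "To establish rates of acute lung toxicity (pneumonitis) with 1-week SIB radiotherapy compared with standard 3-week SIB radiotherapy in patients receiving IMC radiotherapy".

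Section 10.1 then sizes the analysis. The grade ≥3 rate "is anticipated to be 2% in the control group and we want to rule out an increase of 3% (to 5%) or more" with 1-week treatment. Both 1-week groups are pooled, and the method is an A'Hern "single stage design with 90% power and a 5% one-sided significance level", giving 311 test-group IMC patients. Control IMC rates are looked at "for the purpose of confirming the design assumptions but this will be a non-comparative analysis".

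Section 10.5 makes the boundary an IDMC stopping guideline and has observed control rates considered against the design assumptions. Section 10.4 plans to publish this analysis before the primary endpoint, as reassurance about the safety of five fractions. Section 10.4 also contains a general between-group comparison of toxicity frequencies that does not mention IMC patients. Section 10.2 stratifies randomisation by "need for nodal radiotherapy (none, nodes not including IMC or nodes including IMC".

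The skin-toxicity threshold in the early side-effects sub-study has the same form: "The same number of patients will be included from the control group to confirm the design assumptions, but this will be a non-comparative analysis".

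**The concern.** A test against a fixed 5% shows whether the 1-week rate is below 5%. It does not show whether that rate is higher than the 3-week rate. The two questions coincide only through the assumed 2% in control.

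That assumption is uncertain on the protocol's own figures. Section 1.1 gives up to 2% for symptomatic pneumonitis in patients having radiotherapy to these nodes, while section 10.1 assumes 2% for grade ≥3. If grade ≥3 cases are only part of the symptomatic ones, the control rate could be lower, and the fixed limit would then tolerate more than the intended increase.

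The documents do not say how the result is to be read if control departs from 2%, beyond the IDMC taking it into account. Because the result is to be published early as reassurance, a met threshold could be read as an answer to the comparative aim.

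**Working it through.** **Inputs.** From section 10.1: 2% anticipated, 5% to be excluded, 90% power, 5% one-sided, n=311, and 5% not excluded if more than 9 cases occur. From section 10.5: 9 or more cases triggers the guideline. From sections 5.1, 10.1 and 10.2: 4830 patients, 1:1:1 allocation, 10–15% IMC.

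**1. The plan's own figure.** The smallest n and cut-off c with P(X ≤ c | 5%) ≤ 0.05 and P(X ≤ c | 2%) ≥ 0.90 (exact binomial) is n=311, c=9. P(X ≤ 9 | 311, 5%) = 0.0497 and P(X ≤ 9 | 311, 2%) = 0.902. The design is reproduced.

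**2. The two boundaries.** Passing with 9 cases (10.1) gives alpha 0.0497 and power 0.902. Failing with 9 cases (10.5) means passing with 8 or fewer, which gives alpha 0.025 and power 0.826. The sections describe different rules.

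**3. What the fixed limit allows.** The tolerated increase is 5% minus the control rate: 3 points at 2%, 4 points at 1%, 4.5 points at 0.5% and 1 point at 4%.

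**4. Chance of meeting the criterion, P(X ≤ c | 311, test rate).** The rule contains no control data, so only the test rate enters. Rates other than 2% and 5% are illustrative.

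| Control | Test | Increase | Pass, c=9 | Pass, c=8 |
|---|---|---|---|---|
| 2% | 5% | 3 points | 0.050 | 0.025 |
| 1% | 4% | 3 points | 0.201 | 0.123 |
| 0.5% | 3.5% | 3 points | 0.349 | 0.238 |
| 1% | 3% | 2 points | 0.543 | 0.410 |
| 0.5% | 2.5% | 2 points | 0.746 | 0.624 |
| 4% | 4% | none | 0.201 | 0.123 |

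The last row means failing with probability 1 − 0.201 = 0.80 (c=9) or 1 − 0.123 = 0.88 (c=8) although the arms do not differ.

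**5. The comparator already in the trial.** With 311 pooled test patients at 2:1, control has about 311/2 ≈ 155. At 2% in both arms, the 95% half-width for the difference is 1.96 × √[0.02 × 0.98 × (1/311 + 1/155)] = 1.96 × 0.0138 ≈ 0.027, or ±2.7 points.

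**6. Whether a powered comparison is possible.** The setting is a 3-point margin, 2% in both arms, 2:1 allocation and one-sided 5% (normal approximation). Power is about 70% with 311 v 155, 72% with 322 v 161 (10% IMC share) and 86% with 483 v 241 (15% share). Power of 90% needs 560 + 280 = 840 IMC patients. The expected total is 4830 × 0.10 = 483 to 4830 × 0.15 ≈ 725.

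**The case against.** The strongest reply is that the single-arm design is a disclosed and practical choice. Section 10.1 makes pairwise comparison the default except where indicated, and here it is indicated. The verbs in the aim and objective 5 (characterise, establish rates) promise no powered between-arm test, and step 6 shows that one would not be feasible. That stands, and it is a reason not to replace the powered rule.

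Three stronger readings are tempting, and the documents do not support them.

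- *That the control IMC patients are ignored.* They are not. Sections 10.1 and 10.5 both have their rates considered, and RTOG lung toxicity is a secondary endpoint in all arms (10.3).
- *That section 10.4 contradicts the non-comparative statements.* The general toxicity comparison and the two threshold analyses can coexist. What can be said is that 10.4 is not tied to the IMC stratum.
- *That a statistically significant excess would readily pass.* The only passing result with Fisher p<0.05 is 9/311 v 0/155 (+2.9 points, Newcombe 95% CI 0.1 to 5.4, p=0.033). One control event gives p=0.18, and 9 cases already triggers the 10.5 guideline. At 8/311 v 0/155, p=0.057. With true rates of 2.5% and 0.5%, the chance of that single result is (0.746 − 0.624) × 0.460 ≈ 0.056. Pooling the skin groups to reach significance is not legitimate either, because 10.1 judges each test group separately, and 5/103 v 0/103 gives p=0.059.

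Two limits of the added estimate also stand. Follow-up runs from treatment start, so at 3 months control has about two weeks less post-treatment observation. Safety analyses go by treatment received (10.4), so the contrast is not strictly the randomised one.

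**Conclusion.** The point holds as a mismatch between question and analysis. The powered IMC rule is correctly calculated, but it answers the comparative aim only if the control grade ≥3 rate is close to 2%. If control is 1% or 0.5%, the chance of passing despite a true 3-point increase rises from 5% to 20% or 35% at the section 10.1 cut-off. If both rates are 4%, the rule fails about 80% of the time with no difference. These departures from 2% are assumptions chosen for illustration, and the documents do not give the true control rate.

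A supporting difference with its interval can be had from data the trial already collects. At ±2.7 points around 2% it is imprecise and could not by itself show that rates are no higher. The change is therefore an inexpensive improvement and does not imply that the safety rule is invalid.

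**What to change.** 1. Keep the A'Hern boundaries as the powered rule and IDMC guideline. Reconcile the pneumonitis boundary between section 10.1 (more than 9) and section 10.5 (9 or more).
2. In sections 10.1 and 10.4 add, in substance: *The difference in grade ≥3 pneumonitis between the pooled 1-week groups and control, among patients in the IMC randomisation stratum, will be reported with a 95% CI as a supporting estimate for objective 5. This estimate is not powered.* Name the analysis set and note the difference in post-treatment observation time.
3. Give the same estimate to the IDMC with the threshold result (10.5).
4. State that meeting the fixed threshold alone will not be reported as showing rates no higher than with 3-week radiotherapy.
5. The same descriptive difference, for each test group separately against control, can accompany the skin-toxicity threshold in the sub-study.

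The cost is protocol or SAP wording and one extra table per analysis, with no added patients or data. The downside is that the estimate is imprecise, so the published conclusion may have to be more cautious.
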